4.10.1.4 Multiple Comparisons/Multiplicity

No multiplicity adjustment is needed for this study as there is only one primary efficacy endpoint, no repeated analysis of the primary endpoint and each Health Authority will base the statistical analysis of the primary endpoint on either the FDA or EMA approach described in this SAP.

4.10.1.5 Interim Analyses

Not applicable.

4.10.1.6 Examination of Subgroups

Subgroup analyses will be performed for the ITT Analysis Set to examine primary efficacy endpoint BOR up to Week 28 by CCL index, tumor grade, geographical region, gender, age group ($< 60, \ge 60$ years), race, Ann Arbor stage, bone marrow involvement at baseline (Present, Absent) and baseline serum LDH concentration at baseline (Low/Normal, High). Difference in BOR up to Week 28 probabilities along with 90% and 95% CI will be performed using the unstratified exact score method by Chan 1999⁹ by subgroups will be presented in forest plots.

A summary of AE infusion related reaction (IRR) will be provided for subgroups CCL, tumor grade and geographical region. For details refer to Section 4.11.2.

[name] S.A	
Protocol RI-01-006	

4.10.2 Analysis of the Primary Efficacy Endpoint / Variable

4.10.2.1 Main Analysis of the Primary Efficacy Endpoint / Variable

The main analysis will be performed for the ITT Analysis Set and the primary efficacy endpoint / variable (BOR up to Week 28) is defined in Section 3.2.1.1 (with non-response for subjects without any valid post-baseline tumor assessment up to Week 28).

Statistical hypotheses

With

 $\pi_{\text{DRL}_{\text{RI}}}$ denoting the true probability for BOR up to Week 28 in the DRL_RI treatment group

 $\pi_{MabThera^{(B)}}$ denoting the true probability for BOR up to Week 28 in the MabThera[®] treatment group

and $\delta = \pi_{\text{DRL}_\text{RI}} - \pi_{\text{MabThera}^{\circledast}}$ denoting the BOR up to Week 28 probability difference, the null hypothesis is

 $H_0: |\delta| \ge 0.17,$

verbally: DRL_RI is not biosimilar (is either inferior or superior) to MabThera[®] applying pre-specified symmetrical biosimilar margins $\pm 0.17 (\pm 17\%)$.

The alternative hypothesis is

 $H_A: |\delta| < 0.17,$

verbally: DRL_RI is biosimilar (is neither inferior nor superior) to MabThera[®] applying pre-specified symmetrical biosimilar margins $\pm 0.17 (\pm 17\%)$.

Statistical analysis method

Two-sided 90% and 95% CIs for the BOR up to Week 28 probability difference ((DRL_RI minus MabThera®) will be obtained by the unstratified exact score method (Chan 1999⁹) implemented in SAS Proc FREQ.

For FDA, biosimilarity will be concluded (i.e., the null hypothesis rejected) if the 90% CI is completely contained within the pre-defined interval (-0.17, 0.17).

For EMA, biosimilarity will be concluded (i.e., the null hypothesis rejected) if the 95% CI is completely contained within the pre-defined interval (-0.17, 0.17).

4.10.2.2 Sensitivity Analyses of the Primary Efficacy Endpoint / Variable

4.10.2.2.1 Stratified Analysis for Primary Efficacy Endpoint / Variable

Statistical Hypotheses

For the stratified analyses, the hypotheses will be as follow:

With

 $\pi_{\text{DRL}_\text{RI},j}$ denoting the true probability for BOR up to Week 28 in the DRL_RI treatment group in stratum j, $1 \le j \le 18$ (for the 18 strata used in the stratified randomization)

 $\pi_{\text{MabThera}^{\mathbb{B}},j}$ denoting the true probability for BOR up to Week 28 in the MabThera[®] treatment group in stratum j, $1 \le j \le 18$ (for the 18 strata used in the stratified randomization)

and $\delta = \pi_{\text{DRL}_\text{RI,j}} - \pi_{\text{MabThera}^{\circledast},j}$ denoting the common BOR up to Week 28 probability difference (common across the 18 strata used in the stratified randomization),

[name] S.A Protocol RI-01-006

the null hypothesis is

 $H_0: |\delta| \ge 0.17,$

verbally: DRL_RI is not biosimilar (is either inferior or superior) to MabThera[®] applying pre-specified symmetrical biosimilar margins $\pm 0.17 (\pm 17\%)$.

The alternative hypothesis is

 $H_A: |\delta| < 0.17,$

verbally: DRL_RI is biosimilar (is neither inferior nor superior) to MabThera[®] applying pre-specified symmetrical biosimilar margins ± 0.17 ($\pm 17\%$).

Statistical analysis method

Two-sided 90% and 95% CIs for the BOR up to Week 28 common probability difference between treatment groups (DRL_RI minus MabThera®) will be obtained using the stratified Mantel-Haenszel method^{10,11}, stratified by the strata used in the stratified randomization and implemented in SAS Proc FREQ. This analysis will be performed for the ITT analysis set.

4.10.2.2.2 Intercurrent Events

Table 1 and Table 2 lists the intercurrent events (ICEs) identified as relevant for BOR up to Week 28 for FDA and EMA respectively.

Table 1 Intercurrent Events for FDA

Intercurrent Event for FDA

Death prior to first post-baseline radiologic tumor examination

Missing scheduled post-baseline radiologic tumor examination up to Week 28 (for reason other than death)

- reason not related to COVID-19 pandemic
- reason related to COVID-19 pandemic

Initiation of forbidden treatment for LTB-FL prior to Week 28 radiologic tumor examination

Concomitant administration of any other experimental drug or a concomitant chemotherapy, anticancer hormonal therapy, radiotherapy, or immunotherapy is prohibited during study participation. This includes administration of rituximab not included in the protocol scheduled treatment. The relevant eCRF data will be reviewed by medical experts to identify forbidden treatments per the above definition. The programming team will use that information to derive the forbidden treatment ICE.

Table 2 Intercurrent Events for EMA

Intercurrent Event for EMA

Death prior to first post-baseline radiologic tumor examination

- reason for death known to be other than progressive disease
- reason for death progressive disease or unknown

Discontinuation of study treatment prior to first post-baseline radiologic tumor examination

- reason not related to COVID-19 pandemic
- reason related to COVID-19 pandemic

[name] S.A Protocol RI-01-006

Statistical Analysis Plan

Intercurrent Event for EMA

Missed or delayed study drug administration prior to Week 28 radiologic tumor examination

- reason not related to COVID-19 pandemic
- reason related to COVID-19 pandemic

Missing scheduled post-baseline radiologic tumor examination up to Week 28 (for reason other than death)

- reason not related to COVID-19 pandemic
- reason related to COVID-19 pandemic

Initiation of forbidden treatment for LTB-FL prior to Week 28 radiologic tumor examination

Concomitant administration of any other experimental drug or a concomitant chemotherapy, anticancer hormonal therapy, radiotherapy, or immunotherapy is prohibited during study participation. This includes administration of rituximab not included in the protocol scheduled treatment. The relevant eCRF data will be reviewed by medical experts to identify forbidden treatments per the above definition. The programming team will use that information to derive the forbidden treatment ICE.

[name] S.A Protocol RI-01-006

Statistical Analysis Plan

4.10.2.2.3 Main and Sensitivity Estimands

Table 3 describes main and sensitivity estimands for the FDA.

Table 3 Main and Sensitivity Estimands for FDA

Table 4 describes main and sensitivity estimands for the EMA.

Table 4 Main and Sensitivity Estimands for EMA

CCI	DRL_RI and MabThera [®]
CCI	CCI
CCI	
CCI	CCI

CCI Effective Date: 26 Nov 19 CCI CONFIDENTIAL

AL Project Document Version No. 4.0 Project Document Effective Date: Date of last signature Page 31 of 65

[name] S.A Protocol RI-01-006 Statistical Analysis Plan 1 CONFIDENTIAL **Project Document Version No.** 4.0 Effective Date: 26 Nov 19 Project Document Effective Date: Date of last signature Page 32 of 65

4.10.2.2.4 Statistical Hypotheses

$\pi_{\rm DRL}$ RLi		
$\pi_{\mathrm{MabThera}^{\circledast},\mathrm{i}}$		
$\delta = \pi_{\mathrm{DRL}_\mathrm{RI,i}} - \pi_{\mathrm{MabThera}^{\circledast},\mathrm{i}}$		
$H_0: \delta \ge 0.17_{\blacksquare}$		
$H_A: 0 < 0.17$		
CCI	CONFIDENTIAL	Project Document Version No. 4.0
Effective Date: 26 Nov 19	Project D	ocument Effective Date: Date of last signature
CCI	Ŭ	Page 33 of 65

Statistical analysis method

For the final resulting dataset, SAS Proc FREQ will be used to obtain the point estimate and its standard error for BOR up to Week 28 common probability difference (using the stratified Mantel-Haenszel method^{10,11}, stratified by the strata used in the stratified randomization) between treatment groups.

Finally, the two-sided 90% CI for BOR up to Week 28 common probability difference reflecting the strategies for handling ICEs in the main estimand for FDA will be obtained and compared to the bio similarity margins for either rejecting or accepting the null hypothesis.

4.10.2.2.6 Analysis of Main Estimand for EMA

[name] S.A Protocol RI-01-006

Statistical Analysis Plan

MI prediction and imputation steps assuming MAR

MI prediction and imputation steps with specific MNAR rules

Table 6 MI Prediction Model with MNAR for Main Estimand for EMA

Effective Date: 26 Nov 19

CONFIDENTIAL Project Document Version No. 4.0 Project Document Effective Date: Date of last signature Page 36 of 65

[name] S.A Protocol RI-01-006		
CCI		
CCI		
	CCI	
CI		
7		
CCI		
	CC I	
ССІ		
CCI CCI		
CCI		0
		Ū
CCI		
CCI		

[name] S.A Protocol RI-01-006

Statistical Analysis Plan

[name] S.A Protocol RI-01-006

Statistical Analysis Plan

Table 8 MI Prediction Model with MNAR for Sensitivity Estimand for FDA

4.10.2.2.8 Analysis of Sensitivity Estimand for EMA

[name] S.A Protocol RI-01-006

Statistical Analysis Plan

4.10.2.3 Supplementary Analyses of the Primary Efficacy Endpoint / Variable

Supplementary analyses will be performed to further explore the robustness of statistical results for the primary efficacy endpoint.

4.10.2.3.1 Tipping point analysis

Graphical displays, based on the "tipping-point" analysis introduced by Yan 2009¹² and not requiring the MAR assumption, will be used to visualize the results of a two-dimensional set of sensitivity analyses using different imputations (either "response" or "non-response") for missing binary BOR up to Week 28 (per derivation in Section 3.2.1.1) values for comparison of the two treatment groups. All possible combinations of imputations of missing binary primary endpoint values in the DRL-RI and MabThera[®] treatment groups will be evaluated by the statistical method described in Section 4.10.2.1.

Figure 2 below displays a generic example with 8 missing binary endpoint values in the "Treatment Group" (one can impute 0 to 8 successes) and 11 missing binary endpoint values in the "Control group" (one can impute 0 to 11 successes), leading to a matrix of 108 (= 9 times 12) combinations to be tested. For the example displayed in Figure 2, 10 combinations close to the upper left upper corner "worst case" (all missing values in the "Control Group" were imputed as successes and all missing value in the "Treatment Group" were imputed as failures) did not lead to a significant test result (rejection of the null hypothesis).

[name] S.A Protocol RI-01-006

Statistical Analysis Plan

Figure 2 Example for a Tipping Point Analysis Summary Display

"Enhanced tipping-point displays" (Liublinska 2014¹³) will be provided as compact summaries of conclusions drawn from different alternative assumptions.

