At Month 7, Arm A had an overall remission rate of 6%. Arm B had an ORR of 77%, with a complete response (CR) + unconfirmed complete response (CRu) of 47% and partial response (PR) of 30%. Arm C had a CR + CRu of 60% and a PR of 29% (ORR=88%). There were also differences observed in 3-year progression-free survival (PFS) between Arm B and the other 2 arms with the highest PFS rate in Arm C, followed by Arm B, then Arm A. A statistically significant treatment difference was observed for the comparison between Arm C and Arm B (HR 0.53 [95% CI 0.32-0.87; p=0.011], and for the comparison between Arm B and Arm A (HR 0.55 [95% CI 0.37-0.83; p=0.0034]). These data indicate that initial treatment with rituximab significantly delays the need for new therapy.⁹

Another study, RESORT, looked at the role of maintenance therapy in subjects with LTB-FL who received single agent rituximab.¹⁰ Subjects received weekly doses of rituximab (375 mg/m² of BSA) for 4 weeks, and responders were randomised to maintenance rituximab (MR single- dose rituximab every 3 months) or rituximab retreatment (RR - rituximab weekly for 4 weeks at disease progression). The primary endpoint was time to treatment failure (TTF). A total of 384 subjects enrolled. Complete response or PR was achieved in 274 subjects (71%), who were then randomised to MR (n=140) or RR (n=134). The mean number of rituximab doses/subject (including the 4 induction doses) was 15.5 (range 5 to 31) for MR and 4 (range 4 to 16) for RR. With a median follow-up of 3.8 years, TTF was 3.9 years for MR versus 3.6 years for RR (p-value=0.8). At 12 months post randomisation, there was no discernible difference in health -related quality of life and anxiety between the 2 arms.

2.2.4 [name] (DRL_RI)

[name] (DRL) is developing a proposed biosimilar version of the chimeric anti-CD20 monoclonal antibody (mAb), rituximab (DRL_RI).

DRL_RI is a chimeric human/murine IgG1 kappa mAb consisting of murine light and heavy chain variable regions and human constant region sequences. The molecule is composed of 2 heavy chains of 451 amino acids each and 2 light chains of 213 amino acids each with a molecular weight of 145 kDa. Each of the heavy chains contains one N-linked glycan (resulting in 2 N-linked glycans per molecule).

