3.2 Definition of Endpoints / Variables

3.2.1 Definition of Efficacy Endpoints / Variables

3.2.1.1 Definition of the Primary Efficacy Endpoint / Variable

BOR up to Week 28 is defined as the best overall response at any radiologic tumor evaluations (based on central radiology review applying the Cheson 1999² response criteria for malignant lymphoma) up to the end of the allowed window for the Week 28 evaluations. Unscheduled and early termination evaluations will be only considered if they are complete and performed up to the end of the allowed window for the Week 28 evaluations.

[name] S.A	
Protocol RI-01-006	

The primary efficacy endpoint used in the statistical analysis is a binary (response / non-response) BOR up to Week 28 version is defined below. The impact of Intercurrent Events on binary BOR up to Week 28 is not described here but in Section 4.10.2.

For subjects with known tumor response at both Week 12 and Week 28, the definition of binary version of BOR up to Week 28 (the primary efficacy endpoint in the statistical analysis) is:

Response at Week 12	Response at Week 28	Binary version of BOR up to Week 28
CR, CRu or PR	Any known	Response
Any Known	CR, CRu or PR	Response
SD or PD	SD or PD	Non-Response

For subjects with a missing / unknown ("unknown" covers "not evaluable", "not available", "subject not anymore in the study", etc.) tumor response at Week 12 or at Week 28 and tumor response known at the other time-point, the definition of binary version of BOR up to Week 28 is:

Response at Week 12	Response at Week 28	Binary version of BOR up to Week 28
CR, CRu or PR	Missing / Unknown	Response
Missing / Unknown	CR, CRu or PR	Response
SD or PD	Missing / Unknown	Non-Response
Missing / Unknown	SD or PD	Non-Response

For subjects with only missing / unknown tumor responses, the definition of binary version of BOR up to Week 28 is:

Response at Week 12	Response at Week 28	Binary version of BOR up to Week 28
Missing / Unknown	Missing / Unknown	• Non-Response for main analysis using the exact score method, sensitivity analysis using stratified Mantel- Haenszel method, and FDA main estimand
		• Missing for sensitivity analyses within the estimand framework (except FDA main estimand) using multiple imputation approaches and for supplementary analyses as described in Section 4.10.2.3

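### The tipping-point grid in SAP 4.10.2.3.1 leaves out subjects with stable disease at Week 12 and an unknown Week 28 response, although their best response is not settled

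*SAP*

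**What the plan says.** SAP 4.10.2.3.1 describes a two-dimensional tipping-point display that does not rely on the missing-at-random (MAR) assumption. It imputes response or non-response in all combinations "for missing binary BOR up to Week 28 (per derivation in Section 3.2.1.1) values for comparison of the two treatment groups" and evaluates each combination by the main method, the unstratified exact score interval of 4.10.2.1.

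SAP 3.2.1.1 decides which values are missing:

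- Response at Week 12, Week 28 unknown: "CR, CRu or PR Missing / Unknown Response".
- SD or progressive disease (PD) at Week 12, Week 28 unknown: "SD or PD Missing / Unknown Non-Response". SD and PD share one row.
- Both time points unknown: this case is introduced by "For subjects with only missing / unknown tumor responses, the definition of binary version of BOR up to Week 28 is". It is the only one in which the binary value can be missing. It is then missing for the estimand analyses (other than the FDA main estimand) "using multiple imputation approaches and for supplementary analyses as described in Section 4.10.2.3".

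Unknown is defined broadly and includes scans that cannot be evaluated and subjects who have left the study.

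Two further statements bear on scope. SAP 3.2.1.1 warns that "The impact of Intercurrent Events on binary BOR up to Week 28 is not described here but in Section 4.10.2". SAP 4.10.2.2.2 lists, for both FDA and EMA, the intercurrent event "Missing scheduled post-baseline radiologic tumor examination up to Week 28 (for reason other than death".

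**The concern.** The endpoint is best response at any evaluation up to Week 28. A response at Week 12 settles it; SD at Week 12 does not, because a response at Week 28 would still make the subject a responder. Study drug is scheduled at Weeks 12 and 20, before the Week 28 scan, so a later response is possible. Protocol 8.2 itself says that a missed assessment leaves disease status at that time point undetermined.

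A tipping-point grid is meant to show how adverse the unobserved outcomes must be before the conclusion changes. If some of them are fixed as failures in both arms, the grid stops short of the true worst corner. In an equivalence trial that is not automatically conservative, since shared failures can pull the difference towards zero. A reader who sees every cell pass could conclude that no assignment of the unobserved outcomes overturns equivalence, when only part of them has been varied.

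**Working it through.** **The plan's own figure.** The SAP example has 8 and 11 missing values: (8 + 1) × (11 + 1) = 108 combinations, as stated. The grid is complete for the set it uses; the question is which subjects belong to that set.

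**Which subjects are varied** (from 3.2.1.1):

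| Week 12 | Week 28 | Binary value | Settled by the data? | In the grid? |
|---|---|---|---|---|
| Response | Unknown | Response | Yes | Not needed |
| PD | Unknown | Non-response | Later response less plausible | No |
| SD | Unknown | Non-response | No | **No** |
| Unknown | Unknown | Missing | No | Yes |

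**How many subjects.** The documents give no counts, so these rates are assumptions.

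- Arm size: 156 (SAP 4.13.2).
- Share with Week 12 known and Week 28 unknown: 5% to 20% (assumed).
- Week 12 response: 71% to 88% (assumed). The ends are borrowed from the 71% response after induction in one cited study (Protocol 2.2.3) and the 88% expected reference rate (SAP 4.10.2.3.4). Week 12 non-responders are then 12% to 29%, all treated as SD.

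Count per arm = 156 × (share with Week 28 unknown) × (share with SD):

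- Low: 156 × 0.05 × 0.12 = 0.9
- Middle: 156 × 0.10 × 0.20 = 3.1
- High: 156 × 0.20 × 0.29 = 9.0

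That is about 1 to 9 per arm. Each subject moves the worst-corner difference by 1/156 = 0.64 points, so 1 to 9 subjects move it by 0.6 to 5.8 points.

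**An assumed example.** Observed responders are 122 (DRL_RI) v 128 (MabThera), a difference of -6/156 = -3.8 points. Each arm has 4 both-unknown and 4 SD-then-unknown subjects. In the worst corner no DRL_RI unknowns respond and all MabThera unknowns do. Intervals are Miettinen-Nurminen score intervals, which approximate the planned exact score interval.

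| Worst corner | Responders | Difference | 90% lower | 95% lower |
|---|---|---|---|---|
| Plan's grid (5 × 5 = 25 cells) | 122 v 132 | -6.4% | -13.7% | -15.1% |
| Grid extended to SD-then-unknown (9 × 9 = 81 cells) | 122 v 136 | -9.0% | -16.1% | -17.5% |

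Against the -17% margin, every cell of the plan's grid passes. In the extended grid the corner fails at 95% (EMA) and passes at 90% (FDA). The neighbouring cells, 122 v 135 and 123 v 136, have 95% lower bounds of -16.9% and -16.8% and pass. Only the single extreme cell fails.

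**When it could matter.** Take an 80% MabThera rate (125/156) and no both-unknown subjects. The table gives the number of MabThera SD-then-unknown subjects who must become responders, with none in DRL_RI, before the lower bound reaches -17%. Counts up to 12 were tried.

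| Observed difference | 90% interval | 95% interval |
|---|---|---|
| 0 | not reached | not reached |
| -1.9 points | not reached | 11 |
| -3.2 points | 11 | 8 |
| -5.1 points | 7 | 5 |
| -6.4 points | 5 | 3 |

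With 1 to 9 such subjects per arm and no both-unknown subjects, the omission bites mainly at observed differences of about 5 points or more. Both-unknown subjects already in the grid lower that threshold, as the example shows.

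**The case against.** The strongest reply is definitional. The SAP defines best response over the evaluations actually made, so a subject whose only evaluation is SD has an observed best response of SD. Treating it as missing asks what full follow-up would have shown. That is a fair defence of the main derivation, which should stay. It does not answer the point about a sensitivity display whose purpose is to ask that very question.

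A reader might also infer more than the documents support:

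- *That most late missingness escapes testing.* No counts are given. Under the assumed rates, 71% to 88% of subjects with only Week 28 unknown would already be Week 12 responders, with nothing left to vary. Complete unscheduled and early-termination scans within the Week 28 window also count, and subjects who stop drug for reasons other than progression continue scheduled tumour assessments. Both shrink the group.
- *That these subjects are never stress-tested.* A missed scheduled scan is an intercurrent event for both agencies, in wording that can cover Week 28 alone. Multiple imputation under MAR and under specified not-at-random rules is planned, but those rules are redacted. Coverage there can be neither confirmed nor excluded.
- *That 4.10.2.3.3 and 4.10.2.3.4 need the same change.* They do not. Imputing SD-then-unknown subjects at 5.8% barely differs from non-response. The 0.71 and 0.88 probabilities are overall rates, unsuited to subjects already seen not to respond at Week 12.
- *That the cited 71% and 88% give a conversion rate for SD subjects.* They come from different studies, regimens and assessment times. They show at most that later response is plausible.

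It also stands that the example's counts are assumed and that its failure is confined to one cell and one agency's criterion.

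**Conclusion.** The gap is real and can be read from unredacted text: the tipping-point grid varies only subjects with both responses unknown and holds SD-then-unknown subjects as non-responders throughout. The primary analysis is not in error, and nothing here shows that the equivalence conclusion would change. What is affected is how far the visible display can be trusted as a worst case. The size (about 1 to 9 subjects per arm, 0.6 to 5.8 points at the corner) rests on assumed scan-missingness and Week 12 response rates, and the bounds rest on a score approximation to the exact interval. The redacted estimand analyses may already cover part of this. It is a cheap improvement.

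**What to change.** In SAP 4.10.2.3.1 only, add a sentence: for the tipping-point display, a subject is also varied if no CR, CRu or PR and no PD was seen, the only known response is SD, and the other scan (in practice Week 28) is missing or unknown. Keep PD plus missing as non-response. Leave the main analysis, 4.10.2.3.3 and 4.10.2.3.4 unchanged.

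The cost is that sentence, a larger grid (81 cells instead of 25 in the example) and a robustness display that may look less favourable.
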